8.1 EFFICACY ASSESSMENTS

8.1.1 Response Assessments

Efficacy assessments will be performed at the timepoints specified in the SoA (Section 1.2) and must be conducted in accordance with the separate Laboratory Manual and the SoA (Section 1.2).

Response assessments will be at the end Cycle 3, Cycle 5, Week 32, or end of Cycle 8, then every 3 cycles after Week 32 up to 2 years and at the final visit. Week 32 response assessment is the critical efficacy timepoint and should occur regardless if it coincides with end of Cycle 8. Aspects of hematology will be used for response assessment, and hence will be highlighted as response assessments below at Week 32 and final visit.

If Week 32 occurs prior to the end of Cycle 8 (e.g., as a result of a dose delay) and there is a significant gap between Week 32 and Cycle 11 Day 28 (and Cycle 14 Day 28 for bone marrow assessment), an unscheduled visit may be requested by the Medical Monitor for completion of response assessments at the discretion of the investigator.

For ruxolitinib-naïve patients, efficacy of idasanutlin will be assessed by composite response (Hct control and $\geq 35\%$ reduction in spleen volume) in patients with splenomegaly and Hct control alone in patients without splenomegaly. Efficacy in terms of Hct control, CHR, and the 2009 ELN hematologic response criteria for PV (see Appendix 2) will also be assessed in all ruxolitinib-naïve patients regardless of the presence of splenomegaly.

For ruxolitinib-resistant or intolerant patients, efficacy will be assessed by Hct control, CHR, and the 2009 ELN hematologic response criteria.

Spleen volume and length should be measured by CT or MRI scans according to standard procedures. The same radiographic assessment modality must be used for all response evaluations to ensure consistency across different timepoints (including unscheduled assessments). Routine MRI (or CT) within 7 days of screening does not need to be repeated if it meets the study specifications (i.e., Day -35 to Day -1). Details regarding imaging procedures are provided in the Imaging Manual.

8.1.2 Clinical Outcome Assessments

In this study, COA data will be elicited from patients to fully characterize the clinical profile of the study treatment. Patient experience of disease-related symptoms over the course of treatment will be evaluated with the MPN-SAF TSS (see Appendix 14). In addition, the EORTC QLQ-C30 (see Appendix 15) will be used to evaluate the impact of

treatment on functioning and global health status/*HRQoL*, as well as monitor the experience of treatment-related symptoms. A PGIC (*see Appendix 16*) will be administered after baseline to assess the degree to which patients feel their experience of PV symptoms have improved since starting treatment. The COAs, translated as required in the local language, will be distributed by the Investigator staff and completed in their entirety by the patients at specified timepoints during the study. It is estimated that the assessment measures will take approximately 10–15 minutes to complete.

The COA questionnaires (MPN-SAF TSS, EORTC QLQ-C30, and PGIC) will be completed on paper at the site on C1D1 (MPN-SAF TSS and EORTC QLQ-C30 only), and at C2D1 and the end of Cycle 3, Cycle 5, Week 32 or end of Cycle 8, (whichever comes first), and on Day 28 of every 3 cycles after Cycle 8 up to two years after first dose, and/or at the end of treatment/discontinuation visit. *End of cycle assessments will ensure symptom assessments are aligned to efficacy assessments, which allows for the evaluation of improvement of symptoms at key time points when also looking at efficacy.*

Entries should be reviewed for completeness by the site staff during the visit and the patient should be requested to complete any blank items. Changes to the form should not be made once the patient has left the site visit.

8.1.2.1 Myeloproliferative Neoplasm-Symptom Assessment Form Total Symptom Score (MPN-SAF TSS)

The constitutional symptoms of PV significantly impact social and physical activities, impede on independence and disrupt overall quality of life. Experts in the field devised an assessment form to measure the severity of 17 key symptoms of PV known as the *Myeloproliferative Neoplasm-Symptom Assessment Form (MPN-SAF)* ([Cervantes et al. 2009](#)). More recently, a revised abbreviated version known as the MPN-SAF total symptom score (MPN-SAF TSS) was created focusing on the nine most clinically important PV symptoms from the MPN-SAF (*see Appendix 14*) ([Emanuel et al. 2012](#); [Scherber et al. 2011](#)). These include: early satiety, abdominal discomfort, inactivity, concentration issues, night sweats, itching, bone pain, fever, and weight loss. A tenth symptom, fatigue, is assessed using the “worst” fatigue item from the Brief Fatigue Inventory (BFI). The patient provides a severity score for each additional symptom on a scale of 0 (none/absent) to 10 (worst imaginable).

8.1.2.2 European Organization for Research and Treatment of Cancer Quality of Life-Core 30 (EORTC QLQ-C30) Questionnaire

The EORTC QLQ-C30 is a validated, reliable self-report measure (*see Appendix 15*) ([Aronson et al. 1993](#); [Fitzsimmons et al. 1999](#)). It consists of 30 questions that assess five aspects of patient functioning (physical, emotional, role, cognitive, and social), three symptom scales (fatigue, nausea and vomiting, and pain), global health status/*HRQoL*, and six single items (dyspnea, insomnia, appetite loss, constipation, diarrhea, and financial difficulties) with a recall period of the previous week.

8.1.2.3 Patient Global Impression of Change (PGIC)

The PGIC is a one-item measure that has been used in previous research in PV to assess perceived treatment benefit (*see Appendix 16*) (Mesa et al. 2016). Patients will be asked “Since the start of the treatment you’ve received in this study, your polycythemia vera (PV) symptoms are: ‘very much improved’, ‘much improved’, ‘minimally improved’, ‘no change’, ‘minimally worse’, ‘much worse’, and ‘very much worse’.

8.2 SAFETY ASSESSMENTS

Safety assessments will consist of monitoring and recording AE, including serious adverse events and non-serious adverse events of special interest, performing protocol-specified safety laboratory assessments, measuring protocol-specified vital signs, and conducting other protocol-specified tests that are deemed critical to the safety evaluation of the study.

ECG testing will be monitored at baseline and on treatment as outlined in Section 1.2 and in Section 8.2.3. ECG monitoring will be performed locally to mitigate the potential risk for idasanutlin of supraventricular arrhythmias. In case of emergence of supraventricular arrhythmias the Sponsor needs to be immediately notified as this represents an adverse event of special interest for this protocol Section 8.3.6.

Certain types of events require immediate reporting to the Sponsor, as outlined in Section 8.3.5.2. Planned timepoints for all safety assessments are provided in the SoA (Section 1.2).

8.2.1 Physical Examinations

A complete physical examination will include, at a minimum, assessments of the cardiovascular, respiratory, gastrointestinal, dermatological and neurological, musculoskeletal systems in addition to head, eyes, ears, nose, throat, neck and lymph nodes. Further examination of other body systems may be performed in case of evocative symptoms at the Investigator’s discretion.

Height at baseline and weight at each cycle will also be measured and recorded.

Performance status will be measured using the ECOG Performance Status Scale (Appendix 8).

Any abnormality identified at baseline should be recorded on the General Medical History and Baseline Conditions eCRF.

At subsequent visits (or as clinically indicated), limited, symptom-directed physical examinations should be performed. Changes from baseline abnormalities should be recorded in patient’s notes. New or worsened clinically significant abnormalities should be recorded as adverse events on the Adverse Event eCRF.

8.2.2 **Vital Signs**

Oral temperature, pulse rate, respiratory rate, and blood pressure will be assessed as outlined in the SoA (see Section 1.2).

Blood pressure and pulse measurements will be assessed in a supine position with a completely automated device. Manual techniques will be used only if an automated device is not available. When possible, the same arm should be used for all blood pressure measurements.

Blood pressure and pulse measurements should be preceded by at least 5 minutes of rest for the patient in a quiet setting without distractions (e.g., television, cell phones).

Vital signs (to be taken before blood collection for laboratory tests) will be measured in a supine position after 5-minute rest and will include temperature, systolic and diastolic blood pressure, pulse rate, respiratory rate and body temperature. Three readings of blood pressure and pulse will be taken. The first reading should be rejected. The second and third readings should be averaged to give the measurement to be recorded in the eCRF.

8.2.3 **Electrocardiograms**

Single 12-lead ECGs will be obtained as outlined in the SoA (see Section 1.2) using an ECG machine that automatically calculates the heart rate and measures PR, QRS, QT, and QTc intervals. The ECG should be confirmed as interpretable at site.

To minimize variability, it is important that patients be in a resting position for ≥ 5 minutes prior to the ECG evaluation. Environmental distractions (e.g., television, radio, conversation) should be avoided during the pre-ECG resting period and during ECG recording. ECGs should be performed prior to any scheduled vital sign measurements and blood draws. In some cases, it may be appropriate to repeat abnormal ECGs to rule out improper lead placement as contributing to the ECG abnormality.

For safety monitoring purposes, the Investigator or designee must review, sign, and date all ECG tracings. Paper or electronic copies will be kept as part of the patient's permanent study file at the site. If considered appropriate by Roche, ECGs may be analyzed retrospectively at a central laboratory.

ECG characteristics, including heart rate, QRS duration, and PQ(PR), and QT intervals, will be recorded on the eCRF. QTcB (Bazett's correction), QTcF (Fridericia's correction) and RR will be recorded on the eCRF. Changes in T-wave and U-wave morphology and overall ECG interpretation will be documented on the eCRF. T-wave information will be captured as normal or abnormal, U-wave information will be captured in two categories: absent/normal or abnormal.

For Cycle 3 and beyond, ECGs must be done on Day 1 pre-dose, 4, 6 hours, and prior to the dose on Day 2 (24 hours post Day 1 dose) if there is evidence of QTc prolongation > 30 ms during Cycle 1 and Cycle 2 once the patient has received study medication as compared with the the QTcF interval of the screening ECG. Otherwise, ECGs will NOT be required for Cycle 3 and beyond unless the Investigator considers it necessary on behalf of the patient's safety. An unscheduled ECG can be performed as needed any time.

Allowed ECG sampling assessment windows are as follows:

- Pre-dose assessments: within 2 hours
- Assessments < 2 hours: ± 5 minutes
- Assessments 2–24 hours: $\pm 5\%$ (equal to 3 mins/hr)
- Assessments > 24 hours: ± 2 hours

8.2.4 Clinical Safety Laboratory Assessments

Reference ranges for the study laboratory parameters must be supplied to the Sponsor before the study starts. A list of clinical laboratory tests to be performed is provided in [Appendix 9](#) and these assessments must be conducted in accordance with the separate Laboratory Manual and the SoA (Section 1.2).

The Investigator must review the laboratory report, document this review, and record any clinically relevant changes occurring during the study in the AE section of the CRF. The laboratory reports must be filed with the source documents. Clinically significant abnormal laboratory findings are those which are not associated with the underlying disease, unless judged by the Investigator to be more severe than expected for the patient's condition.

- In the event of unexplained abnormal clinically significant laboratory test values, the tests should be repeated immediately and followed up until they have returned to the reference range and/or an adequate explanation of the abnormality is found.
- If such values do not return to normal/baseline within a period of time judged reasonable by the Investigator, the etiology should be identified and the Sponsor notified.
- If laboratory values from non-protocol specified laboratory assessments performed at the local laboratory require a change in patient management or are considered clinically significant by the Investigator (e.g., SAE or AE or dose-modification) then, the results must be recorded in the CRF.

Results of clinical laboratory testing will be recorded on the eCRF.

Additional blood or urine samples may be taken at the discretion of the Investigator if the results of any test fall outside the reference ranges, or clinical symptoms necessitate additional testing to monitor patient safety.

Where the clinical significance of abnormal lab results is considered uncertain, screening lab tests may be repeated before idasanutlin administration to confirm eligibility.

Based on continuous analysis of the data in this study and other studies, any sample type not considered to be critical for safety may be stopped at any time if the data from the samples collected does not produce useful information.

8.2.5 Suicidal Risk Monitoring

Not applicable.

8.2.6 Medical History and Demographic Data

Medical history includes clinically significant diseases, surgeries, PV history (including prior PV therapies, HU therapy, and phlebotomies), reproductive status and all medications (e.g., prescription drugs, over-the-counter drugs, herbal or homeopathic remedies, nutritional supplements) used by the patient within 28 days prior to the screening visit.

PV has specific constitutional symptoms associated with the disease such as fever, night sweats, pruritus, microvascular disturbances, headaches, abdominal swelling and weight loss. Any specific PV symptoms should be clearly documented if present at baseline in the patients PV Medical History eCRF. Ongoing treatments specific to these conditions should be noted on the Targeted previous and concomitant medicines eCRF.

Demographic data will include age, sex, and self-reported race/ethnicity.

8.3 ADVERSE EVENTS AND SERIOUS ADVERSE EVENTS

The definitions of an AE or serious adverse event (SAE) can be found in [Appendix 10](#). The non-serious adverse events of special interest and disease-related events and/or disease-related outcomes not qualifying as AEs or SAEs are discussed in Sections [8.3.6](#) and [8.3.8](#).

The Investigator is responsible for ensuring that all adverse events (including assessment of seriousness, severity and causality; see [Appendix 10](#)) are recorded on the Adverse Event eCRF and reported to the Sponsor in accordance with instructions provided in this section and in [Appendix 11](#).

Procedures used for recording AEs are provided in [Appendix 11](#) and include:

- Diagnosis versus signs and symptoms
- AEs occurring secondary to other events
- Persistent or recurrent AEs
- Abnormal laboratory values
- Abnormal vital sign values

- Abnormal liver function tests
- Deaths
- Preexisting medical conditions
- Lack of efficacy or worsening of PV
- Hospitalization or prolonged hospitalization
- Clinical outcome assessment data

8.3.1 Time Period and Frequency for Collecting Adverse Event and Serious Adverse Event Information

Investigators are not obligated to actively seek AE or SAE in post-study follow-up. However, if the Investigator learns of any SAE, including a death, at any time after a patient has been discharged from the study, and he/she considers the event to be reasonably related to the study treatment or study participation, the Investigator must promptly notify the Sponsor.

The method of recording, evaluating, and assessing causality of AEs and SAEs and the procedures for completing and transmitting SAE reports are provided in [Appendix 10](#) and [Appendix 11](#).

Investigators will seek information on adverse events at each patient's contact. All adverse events, whether reported by the patient or noted by study personnel, will be recorded in the patient's medical record. Adverse events will then be reported on the Adverse Event eCRF as follows:

After informed consent has been obtained **but prior to initiation of study treatment**, only serious adverse events caused by a protocol-mandated intervention should be reported (e.g., SAE related to invasive procedures such as bone marrow biopsies). Any other adverse event should not be reported.

After initiation of study treatment, all AE, regardless of relationship to study treatment, will be reported until 28 days after the last dose of study treatment.

After a period of 28 days from the last dose of study treatment, Investigators should report any deaths, SAE, or other AE of concern that are believed to be related to prior treatment with study treatment (see Section [8.3.2](#)).

8.3.2 Post-Study Adverse Events and Serious Adverse Events

The Investigator is not required to actively monitor patients for AE after the end of the AE reporting period (defined as 28 days after the last dose of study drug).

8.3.3 Method of Detecting Adverse Events and Serious Adverse Events

Care will be taken not to introduce bias when detecting AEs and/or SAEs. Open-ended and non-leading verbal questioning of the patient is the preferred method to inquire about AE occurrence.

A consistent methodology of non-directive questioning should be adopted for eliciting AE information at all patient evaluation timepoints.

8.3.4 Follow-Up of Adverse Events and Serious Adverse Events

8.3.4.1 Investigator Follow-Up

The Investigator should follow each AE until the event has resolved to baseline grade or better, the event is assessed as stable by the Investigator, the event is otherwise explained, the patient is lost to follow-up, or the patient withdraws consent. Every effort should be made to follow all SAE considered to be related to study treatment or trial-related procedures until a final outcome can be reported.

During the study period, resolution of AE (with dates) should be documented on the AE eCRF and in the patient's medical record to facilitate source data verification. If, after follow-up, return to baseline status or stabilization cannot be established, an explanation should be recorded on the AE eCRF.

All pregnancies reported during the study should be followed until pregnancy outcome and reported according to the instructions provided in Section 8.3.6.

8.3.4.2 Sponsor Follow-Up

For SAE, non-serious adverse events of special interest, and pregnancies, the Sponsor or a designee may follow up by telephone, fax, electronic mail, and/or a monitoring visit to obtain additional case details and outcome information (e.g., from hospital discharge summaries, consultant reports, autopsy reports) in order to perform an independent medical assessment of the reported case.

8.3.5 Regulatory Reporting Requirements for Serious Adverse Events

Prompt notification by the Investigator to the Sponsor of a SAE is essential so that legal obligations and ethical responsibilities towards the safety of patients and the safety of a study treatment under clinical investigation are met. The Sponsor has a legal responsibility to notify both the local regulatory authority and other regulatory agencies and will comply with country-specific regulatory requirements relating to safety reporting to the regulatory authority, Institutional Review Boards (IRB)/Independent Ethics Committees (IEC), and investigators. Investigator safety reports must be prepared for suspected unexpected serious adverse reactions (SUSAR) according to local regulatory requirements and Sponsor policy and forwarded to investigators as necessary.

An investigator who receives an investigator safety report describing a SAE or other

specific safety information (e.g., summary or listing of SAEs) from the Sponsor will review and then, file it along with the Investigator's Brochure and will notify the IRB/IEC, if appropriate according to local requirements.

8.3.5.1 Emergency Medical Contacts

To ensure the safety of study patients, access to the Medical monitors is available 24 hours a day 7 days a week. Medical monitors contact details will be available on a separate list generated by the study management team.

8.3.5.2 Immediate Reporting Requirements from Investigator to Sponsor

Certain events require immediate reporting to allow the Sponsor to take appropriate measures to address potential new risks in a clinical trial. The Investigator must report such events to the Sponsor immediately; under no circumstances should reporting take place more than 24 hours after the Investigator learns of the event. The following is a list of events that the Investigator must report to the Sponsor within 24 hours after learning of the event, regardless of relationship to study treatment:

- Serious adverse events
- Non-serious adverse events of special interest
- Pregnancies (see Section [8.3.6](#))

The Investigator must report new significant follow-up information for these events to the Sponsor immediately (i.e., no more than 24 hours after becoming aware of the information). New significant information includes the following:

- New signs or symptoms or a change in the diagnosis.
- Significant new diagnostic test results.
- Change in causality based on new information.
- Change in the event's outcome, including recovery.
- Additional narrative information on the clinical course of the event.

Investigators must also comply with local requirements for reporting SAE to the local Health Authority and IRB/EC.

8.3.6 Pregnancy

Details of all pregnancies in female patients of childbearing potential and female partners of male patients will be collected after the start of study treatment and for 28 days after the last dose of idasanutlin.

If a pregnancy is reported, the Investigator should inform the Sponsor within 24 hours of learning of the pregnancy and should follow the pregnancy reporting process as detailed in [Appendix 6](#).

Abortions (spontaneous), underlying maternal or embryo fetal toxicities that led to therapeutic or elective abortion, and any congenital anomalies/birth defects are considered SAEs (Appendix 6).

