- 9. Patients must be willing to submit the blood sampling and bone marrow sampling for the PK and pharmacodynamic analyses and exploratory biomarkers.
- 10. Adequate hepatic function assessed by:
 - Serum total bilirubin < 2 mg/dL, unless resulting from hemolysis or known Gilbert's disease.
 - AST/ALT < 2.5 × institutional ULN.
- 11. Adequate renal function assessed by serum creatinine within reference lab normal limits OR creatinine clearance ≥ 50 mL/min calculated by the Cockcroft Gault formula ([Appendix 5](#)).
- 12. Patients must meet all of the general inclusion criteria listed above prior to dosing on Cycle 1, Day 1 (including ECOG and labs checked following initial screening eligibility verification) when screening performed > 72 hours from start of treatment.
- 13. Ability and willingness to comply with the study protocol procedures, including clinical outcome assessment (COA) measures.

Contraception

14. Male and/or female patients

a) Male Patient:

Agreement to use contraceptive measures, and agreement to refrain from donating sperm, as defined below:

With female partners of childbearing potential or pregnant female partners, men must use a condom during the treatment period and for at least 90 days after the last dose of idasanutlin. Men must refrain from donating sperm during this same period.

b) Female Patients:

For women of childbearing potential: agreement to use contraceptive methods that result in a failure rate of < 1% per year during the treatment period and for at least 6 weeks after the last dose of idasanutlin.

A woman is considered to be of childbearing potential if she is post-menarcheal, has not reached a post-menopausal state (at least 12 continuous months of amenorrhea with no identified cause other than menopause), and has not undergone surgical sterilization (removal of ovaries and/or uterus).

Examples of contraceptive methods with a failure rate of < 1% per year include bilateral tubal ligation; male sterilization; established, proper use of hormonal

contraceptives that inhibit ovulation, hormone-releasing intrauterine devices; and copper intrauterine devices.

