4. COLLECTION OF PREGNANCY INFORMATION

- **Male participants with partners who become pregnant**

The Investigator will attempt to collect pregnancy information on any male participant's female partner who becomes pregnant while the male participant is in this study (see Section 8.3.6). This applies only to male participants who receive idasanutlin.

Attempts should be made to collect and report details of the course and outcome of any pregnancy in the partner of a male participant exposed to study drug. After obtaining the necessary signed consent from the pregnant female partner directly, the Investigator will record pregnancy information on the Clinical Trial Pregnancy Reporting Form and submit it to the Sponsor within 24 hours of learning of the partner's pregnancy. The pregnant partner will need to sign an Authorization for Use and Disclosure of Pregnancy Health Information to allow for follow-up on her pregnancy. Once the authorization has been signed, the Investigator will update the Clinical Trial Pregnancy Reporting Form with additional information on the course and outcome of the pregnancy. An Investigator who is contacted by the male participant or his pregnant partner may provide information on the risks of the pregnancy and the possible effects on the fetus, to support an informed decision in cooperation with the treating physician and/or obstetrician. The female partner will be followed to determine the outcome of the pregnancy. Information on the status of the mother and child will be forwarded to the Sponsor. Monitoring of the patient should continue until conclusion of the pregnancy. Any termination of the pregnancy will be reported regardless of fetal status (presence or absence of anomalies) or indication for procedure.

- **Female participants who become pregnant**

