Investigator will collect pregnancy information on any female participant, who becomes pregnant while participating in this study (see Section 8.3.6). Information will be recorded on the appropriate form and submitted to the Sponsor within 24 hours of learning of a participant's pregnancy. The participant will be followed to determine the outcome of the pregnancy. The Investigator will collect follow-up information on the participant and the neonate, which will be forwarded to the Sponsor. Monitoring of the patient should continue until conclusion of the pregnancy. Any termination of pregnancy will be reported, regardless of fetal status (presence or absence of anomalies) or indication for procedure.

While pregnancy itself is not considered to be an AE or SAE, and should not be recorded on the AE eCRF, any pregnancy complication will be reported as an AE or SAE. A spontaneous abortion is always considered to be an SAE and will be reported as such. Any post-study pregnancy related SAE considered reasonably related to the study treatment by the Investigator, will be reported to the Sponsor as described in [Appendix 10](#). While the Investigator is not obligated to actively seek this information in former study participants, he or she may learn of an SAE through spontaneous reporting.

Any female participant who becomes pregnant while participating in the study will discontinue study treatment.

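### Required pregnancy collection ends 28 days after the last dose, before the protocol's own contraception periods end (6 weeks for women, 90 days for men)

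*Protocol*

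**What the plan says.** **Collection.** Protocol Section 8.3.6 covers female patients of childbearing potential and female partners of male patients together. Their pregnancies "will be collected after the start of study treatment and for 28 days after the last dose of idasanutlin".

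**Contraception.** Inclusion criterion 14 in Section 5.1, repeated in the synopsis, sets two longer periods. Women of childbearing potential must use effective contraception "during the treatment period and for at least 6 weeks after the last dose of idasanutlin". For male patients with a partner who is pregnant or could become so, "men must use a condom during the treatment period and for at least 90 days after the last dose of idasanutlin", and sperm donation is barred for the same time.

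**Appendix 6, Section 4.** For both groups it collects pregnancies that occur while the participant is in the study, and each time it refers back to Section 8.3.6. A further sentence on men asks for attempts to collect and report the course and outcome of "any pregnancy in the partner of a male participant exposed to study drug", with no time limit.

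**Follow-up.** Section 8.3.4.1 requires pregnancies reported during the study to be followed to their outcome.

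**The concern.** Criterion 14 shows that the sponsor wants conception avoided for 6 weeks or 90 days after the last dose. If that precaution fails late in the period, Section 8.3.6 as written does not ask for a report. Follow-up to outcome depends on a report having been made, so an unreported pregnancy is not followed either. Pregnancies in this trial will be few, and each documented outcome is useful for an investigational drug that acts on cell-cycle arrest and apoptosis (Section 2.2.2). The point concerns the completeness of safety data. It does not touch the response endpoints.

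**Working it through.** The check compares the stated windows in days after the last dose. No statistical model is involved.

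**Inputs**
- Pregnancy collection: 28 days (Section 8.3.6).
- Contraception, women: at least 6 weeks = 6 × 7 = 42 days (Section 5.1, criterion 14).
- Contraception, men: at least 90 days (same criterion).
- Final visit: 28 days ± 7 days after the last dose, so day 35 at the latest in the ordinary case (Section 4.1.1; Table 1, footnote 14). A withdrawal decided after day 28 moves that visit to about the withdrawal date.

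**Shortfall = contraception period − collection period**

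| | Contraception | Collection | Shortfall | Share of period not covered |
|---|---|---|---|---|
| Women | 42 days | 28 days | 42 − 28 = 14 days | 14/42 = 33% |
| Partners of men | 90 days | 28 days | 90 − 28 = 62 days | 62/90 = 69% |

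A final visit at day 35 would still leave 42 − 35 = 7 days (women) and 90 − 35 = 55 days (men) with no scheduled contact. Because criterion 14 sets minimum periods, these shortfalls are minimum values.

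**Does other text extend the window?**
- Section 8.3.5.2 puts pregnancies on the 24-hour reporting list, but refers to Section 8.3.6 for them.
- Appendix 6 Section 4 limits collection to time in the study and also refers to Section 8.3.6. Its one unlimited sentence concerns partners of exposed men only. For those partners it contradicts the 28-day limit.
- Appendix 6 Section 4 states that a pregnancy is not itself an adverse event, so adverse event reporting does not capture it.
- After day 28, Section 8.3.1 asks for deaths, serious events and other events of concern only if believed related to treatment. Section 8.3.2 requires no active monitoring. Appendix 6 Section 4 treats post-study pregnancy-related serious events the same way.
- Appendix 6 Section 6 makes any birth defect in a child of a female patient, or of an exposed man's partner, a serious adverse event with no stated window. It takes effect only if the site learns of the outcome.

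One case is therefore left without any reporting duty: a pregnancy in a female patient that arises after day 28 but within 42 days, and is uneventful or has a complication not judged related. For partners of men between day 28 and day 90, the protocol gives two conflicting instructions.

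Section 8.3.6 also does not say whether its 28 days refer to conception or to the site becoming aware. If awareness is meant, a conception before day 28 that is recognised later would also fall outside, and the shortfall would be larger than shown.

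**The case against.** The strongest reply is that 28 days is a deliberate and consistent choice. It matches the adverse event reporting period, the safety follow-up and the final visit. A contraception period may be precautionary and need not equal a reporting period. That is fair as far as it goes, but the protocol gives no reason for the difference, and Appendix 6 does not apply the 28 days consistently to partners of men.

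Two stronger readings are tempting and are not supported.
- **That these pregnancies will go uncollected and a safety signal will be missed.** The most the text supports is that they need not be collected. The unlimited Appendix 6 sentence, the birth-defect rule and the reporting of related post-study serious events all leave routes open, and adverse outcomes are the events most likely to use them.
- **That conceptions after day 28 are drug-exposed.** Section 5.1 sets contraception periods and does not call them exposure windows. Section 2.2.2 gives a half-life of about one day, so day 28 is about 28 half-lives after the last dose of parent drug. No half-life is given for the M4 metabolite. The documents do not show exposure that late.

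It is also true that the shortfalls measure calendar time, not missed events. The planned maximum is about 40 + 60 = 100 efficacy-evaluable patients, all told to use contraception if it applies to them, and the documents do not say how many are fertile. Active ascertainment to day 42 or day 90 would need contacts that the schedule lacks. Reporting when the investigator becomes aware would not.

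**Conclusion.** The inconsistency is real and stands in the current text. Required collection falls short of the protocol's own contraception periods by 14 days for women and 62 days for partners of male patients, and it covers 28/42 = 67% and 28/90 = 31% of them. For women, nothing else requires a pregnancy as such to be reported after day 28. For partners of men, Section 8.3.6 and Appendix 6 disagree.

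This rests on reading the 28 days as the limit for when a pregnancy arises, and on participation ending at about the final visit. No number of affected pregnancies can be estimated from the documents, and it is likely to be very small. Sample size, error rates and efficacy results are unaffected. This is a minor but worthwhile correction to safety reporting.

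**What to change.** Reconcile Section 8.3.6 and Appendix 6 Section 4 with criterion 14 in Section 5.1. The text should say that any pregnancy the investigator learns of, in a female patient or a male patient's partner, that arises within the contraception period the protocol already sets for that patient is reported and followed to outcome. It should state that the window refers to when the pregnancy arose, not to when it was reported, and the partner sentence in Appendix 6 should carry the same limit as Section 8.3.6. Patients should be told at the final visit to notify the site of a pregnancy arising in the remaining period.

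The cost is wording, a line in the patient information and a rare additional report. No new scheduled visit is needed, and no change to the contraception periods is proposed.
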